6.1. Primary Immunogenicity Endpoint

The primary immunogenicity endpoint is the anti-CHIKV seroresponse at Day 22 in prior alpha versus naïve alpha subjects, where seroresponse is defined as a 4-fold rise over baseline in anti-CHIKV neutralizing antibodies as determined by a luciferase-based assay (NT80). Note that seroresponse is referred to as seroconversion in the protocol and in the list of endpoints excerpted from the protocol below.

6.1.1. Analysis Methods for Primary Immunogenicity Endpoint

The primary immunogenicity analysis will compare the proportion of prior alpha subjects to the proportion of naïve alpha subjects with seroresponse by anti-CHIKV neutralizing antibody at Day 22. The significance of the comparison of the two groups will be assessed using a Fisher's exact test. The percentage with seroresponse in each group will be presented along with a 95% CI calculated using the Wilson method (Agresti 1998). The difference and a 95% CI for this difference calculated based on Newcombe hybrid score method will also be presented. The primary immunogenicity analysis will be performed on both the IEP and mITT population.

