4.18 Subject Replacement

Subjects who undergo Early Discontinuation at either site before Day 29 may be replaced at the Sponsor's discretion. Should a subject who previously received an alphavirus vaccine withdraw, a replacement for this cohort will be enrolled. If an age and gender-matched alphavirus-naïve subject has already been enrolled for the withdrawn subject, they will not be compelled to leave the study. Should an alphavirus naïve subject who has been age and gender-matched to a prior alphavirus vaccine recipient withdraw, they will be replaced by a new alphavirus naïve subject that is age and gender-matched to the same prior alphavirus vaccine recipient.

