9 STATISTICAL ANALYSIS

9.1 Sample Size Calculation

The sample size here was chosen based on the number of subjects in the Fort Detrick Special Immunization/Special Procedures Program (USAMRIID) who are available for screening. Of the approximately 60 available, 30 are expected to enroll in this trial along with an equal number of alphavirus naïve age- and gender-matched subjects. Based on an interim analysis of this vaccine lot and regimen in Study PXVX0317-001, at least 95% of the alphavirus-naïve controls are expected to seroconvert in this trial. Assuming that the alphavirus-naïve group has a 95% seroconversion rate, a total sample size of 60 subjects affords 80% power to detect a significant difference between groups if the seroconversion rate in the prior alphavirus vaccine recipients is 65% or less. Or, in other words, power is 80% to detect a difference between groups if the seroconversion rate in the prior alphavirus recipients is 30 percentage points lower than in the alphavirus-naïve group. Compared to the previously cited studies in which decrements in the proportion of seroconversion of 64% (McClain 1998) and 100% (Harrison 1971) (DeMeio 1979) were seen, this study is adequately powered to detect immune interference on the order of one-half to one-third of what has previously been described.

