In the event that we have overestimated the willingness of this pool of eligible subjects to participate, the ability to detect differences in the proportion of seroconversion of the same order as was previously shown by McClain (36% versus 95% seroconversion), 10 subjects per group would afford 71% power to detect a significant difference. The power of other combinations of seroconversion rate and sample size can be seen in Table 3. For example, 10 subjects per group afford 81% power to detect a difference between groups if the seroconversion rate is as low as 30% in the prior alphavirus vaccine recipients, while 20 subjects per group provide 89% power to detect a difference if the seroconversion rate is 50% or lower among prior alphavirus recipients. This is certainly less than ideal in terms of designing a field study in an area endemic for other alphaviruses. The decision to conduct such a study will be dependent on many factors and the residual possibility that a lesser degree of immune interference may have gone undetected will have to be considered. If, on the other hand, immune interference on the order of that reported by DeMeio is seen in which a neutralizing antibody response is entirely abrogated, data from this study would be sufficiently compelling to avoid recruiting for field studies in areas co-endemic for other alphaviruses.

Table 3: Power of Detecting a Significant Difference between Prior Alphavirus Vaccine Recipients and Alphavirus-naïve Vaccine Recipients with a 95% Seroconversion Rate

Number of Subjects per Arm	Seroconversion Rate among Prior Alphavirus Vaccine Recipients				
	30%	40%	50%	60%	70%
10	81%	63%	43%	24%	9%
20	> 99%	97%	89%	72%	45%
30	> 99%	> 99%	98%	89%	63%

Power of each combination estimated from a Fisher's exact test comparing the seroconversion rate observed among prior alphavirus vaccine recipients to the rate observed among alphavirus-naïve vaccine recipients assuming the true rate in the latter group is 95%.

With respect to safety as a study endpoint, this study will have 80% power to detect a 30% difference between pre-exposure groups in the incidence of any single or aggregate solicited adverse event expected to occur in 5% of the subjects in one of the groups. With a total of 60 subjects receiving PXVX0317, there is a 95% chance that an uncommon AE – one expected to occur in 5% of vaccinees – will be observed at least once in the trial.

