9.6 Immunogenicity Analysis

All tests will be carried out at a 2-sided significance level of 0.05 and no adjustment for multiplicity will be applied.

Seroconversion Analysis:

The primary immunogenicity analysis will compare prior alphavirus vaccine recipients to alphavirus-naïve controls on the proportion in each group who seroconvert by anti-CHIKV neutralizing antibody at Day 22. Seroconversion is defined as a 4-fold or greater rise over baseline in anti-CHIKV neutralizing antibodies as assessed by a luciferase-based assay.

Specifically, we will test the hypotheses:

$$H_0: P_1 = P_2 \text{ vs. } H_1: P_1 \neq P_2$$

where P_1 and P_2 denote the proportion of subjects who seroconvert in the prior alphavirus vaccine recipients and the alphavirus-naïve controls, respectively.

The significance of the comparison of the pre-exposure groups will be assessed using a Fisher's exact test. The percentage who seroconvert in each group will be presented along with its 95% CI calculated using the Wilson method. A sensitivity analysis of the comparison will be performed using a logistic regression model that incorporates age, gender, and baseline titer as potential predictive factors. Fisher's test comparing seroconversion rates at other time points may also be performed. Similar analyses of the proportion who seroconvert will be conducted on Days 8, 29, 57 and 182 for anti-CHIKV neutralizing antibody and on Days 22 and 29 for total anti-CHIKV, total anti-VEEV and neutralizing anti-VEEV antibodies (secondary endpoints).

Threshold analyses:

The percentage of subjects achieving specified thresholds (e.g., ≥ 40 , 160, and 640 anti-CHIKV antibody titers), and associated Wilson 95% CIs, will also be calculated for Days 1, 8, 22, 29, 57 and 182 for neutralizing antibody and at Days 1, 22 and 29 for total anti-CHIKV, total anti-VEEV and neutralizing anti-VEEV antibodies (secondary end-points). The groups will be compared by pairwise Fisher's exact tests on the percentage achieving each threshold.

GMT analyses:

For the secondary comparisons based on GMT, the hypotheses tested will be

$$H_0: \mu_1 = \mu_2 \text{ vs. } H_1: \mu_1 \neq \mu_2$$

where μ_1 and μ_2 denote the GMT for the prior alphavirus vaccine recipients and the alphavirus-naïve controls, respectively.

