3.1.4. Modified Intent-to-Treat (mITT) Population

The mITT population includes all subjects in the exposed population who have evaluable immunogenicity results from both Day 1 and at least one later on-study sample.

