3.1.5. Immunogenicity Evaluable Population (IEP)

The IEP includes all subjects in the exposed population who:

- Have no important protocol deviation or other reason to be excluded as defined prior to database lock.
- Have not received a prohibited medication.
- Provide evaluable serum sample results for baseline and the primary immunogenicity endpoint within the required time frames:
 - Baseline: Day 1 or within 60 days before study vaccine administration
 - Day 22: Day 19 through Day 25, inclusive

In addition, all subjects in the alphavirus-naïve group are required to be seronegative for both CHIKV and VEEV at baseline, where seronegativity is defined as:

- Anti-CHIKV neutralizing antibody levels below the limit of detection (LOD) of 15, determined by luciferase-based assay (NT80)
- Anti-VEEV neutralizing antibody levels below the LOD of 20, determined by Plaque-Reduction Neutralization Test (PRNT80) assay,

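### Should the primary Day 22 seroresponse comparison use Boschloo's unconditional exact test instead of Fisher's exact test?

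*SAP*

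**What the plan says.** Protocol section 9.6 sets two-sided tests at 0.05 with no multiplicity adjustment and states that "The significance of the comparison of the pre-exposure groups will be assessed using a Fisher" exact test. SAP section 6.1.1 repeats this for the two study arms, "The significance of the comparison of the two groups will be assessed using a Fisher" exact test, and adds an interval estimate: "The difference and a 95% CI for this difference calculated based on Newcombe hybrid score method will also be presented".

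Protocol section 9.1 bases power on the same test. With a naïve rate of 95% and a prior-recipient rate of 65%, "a total sample size of 60 subjects affords 80% power to detect a significant difference between groups". For under-recruitment, with rates of 36% and 95%, "10 subjects per group would afford 71% power to detect a significant difference". The footnote to Table 3 names Fisher's exact test as the basis of every cell.

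Two populations are analysed. The IEP (SAP section 3.1.5) excludes subjects in either arm for important deviations, prohibited medication or samples outside the window, and has one rule for controls only: "In addition, all subjects in the alphavirus-naïve group are required to be seronegative for both CHIKV and VEEV at baseline". The mITT population (SAP section 3.1.4) comprises "all subjects in the exposed population who have evaluable immunogenicity results from both Day 1 and at least one later on-study sample", without that seronegativity rule.

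**The concern.** Fisher's test conditions on both margins of the 2×2 table, but the design fixes only the two group sizes. In small groups, especially with rates near 100%, this leaves much of the 5% error allowance unused. An unconditional exact test can use more of it without exceeding 5%.

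The number of prior recipients is limited by the available pool, and Protocol section 9.1 itself concedes that a smaller degree of interference could be missed. If a different valid test detects moderate interference more often with the same subjects, the plan appears to give up power for nothing. The apparent loss is largest in the protocol's own fallback of 10 per group.

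**Working it through.** **Inputs.** Naïve rate 95%; prior rate 65% (main case) or 36% (fallback); 30 or 10 per arm; two-sided 0.05. The rates and sizes are from Protocol section 9.1, the significance level from section 9.6.

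**Method.** With *a* responders among n₁ prior recipients and *b* among n₂ controls:

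- power = Σ Bin(a; n₁, p₁) · Bin(b; n₂, p₂), summed over the tables the test rejects;
- maximum size = the largest value of the same sum with p₁ = p₂ = p, over all p.

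Fisher rejects tables with two-sided p ≤ 0.05. Boschloo's test, as used here, orders tables by that p-value and takes the largest rejection region whose maximum size is at most 0.05.

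**The plan's figures first, by hand at 10 per arm, 36% versus 95%.** With 10, 9, 8 or 7 naïve responders, Fisher rejects when prior responders number at most 5, 3, 2 or 1. The naïve probabilities are 0.5987, 0.3151, 0.0746 and 0.0105. The prior cumulative probabilities are 0.8928, 0.4868, 0.2405 and 0.0764.

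0.5987×0.8928 + 0.3151×0.4868 + 0.0746×0.2405 + 0.0105×0.0764 ≈ 0.707. The printed figure is 71%.

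Full enumeration at 30 per arm, 65% versus 95%, gives 78.8% against the printed 80%. Table 3 reproduces throughout. Its 30-per-arm row, for example, computes to 100.0, 99.9, 98.2, 89.3 and 63.1%, against the printed >99, >99, 98, 89 and 63%.

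**Boschloo at 10 per arm.** The cut-off on the Fisher p-value rises to 0.0867. This adds the tables 6 v 10, 4 v 9, 3 v 8 and 2 v 7 (prior v naïve responders) and some of negligible probability:

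0.5987×0.0767 + 0.3151×0.2424 + 0.0746×0.2462 + 0.0105×0.1642 ≈ 0.142, so power is about 84.9%.

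**Both tests at the planned sizes.**

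| Prior/naïve n | Rates | Fisher power (max size) | Boschloo power (max size) |
|---|---|---|---|
| 30/30 | 65% v 95% | 78.8% (2.7%) | 83.3% (4.7%) |
| 30/30 | 70% v 95% | 63.1% | 70.1% |
| 30/30 | 75% v 95% | 43.6% | 52.7% |
| 30/30 | 36% v 95% | 99.96% | 99.97% |
| 10/10 | 36% v 95% | 70.7% (1.3%) | 84.9% (4.2%) |

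**How stable is the gain?** At 65% versus 95%, over all 36 pairs of sizes from 25 to 30, it runs from 0.0 to 10.0 points. With 30 controls it is 1.9 points at 28 prior recipients, 0.7 at 27 and 0.0 at 25. Near the fallback, at 36% versus 95%, it is 14.2 points at 10/10, 9.3 at 9/9, 7.2 at 10/9, 8.5 at 11/11 and 0.0 at 12/10. The 10/10 figure is therefore a local peak caused by discreteness.

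**Does the definition matter?** The ordering above rejected everything Fisher rejects at all 36 pairs. Doubling the one-sided Boschloo p-value, another common convention, loses some Fisher rejections at 16 of the 36 and changes power by −3.1 to +10.0 points. At 30 prior and 26 naïve, Fisher has 81.4%, the two-sided ordering 84.2% and the doubled version 78.3%.

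**Is the lost power out of reach otherwise?** Only the prior arm is limited by the pool; Protocol section 4.1.2 recruits controls by public advertising. With Fisher's test and one more control, power is 86.1% at 30/31 (65% v 95%) and 83.7% at 10/11 (36% v 95%).

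**The case for a change.** The best case for changing is that, with the two-sided ordering, Boschloo's test never rejected less than Fisher's at any size checked, kept its maximum size below 5%, and needs no extra subjects. It fits the sampling, since only the group sizes are fixed. At 30 per arm its gain falls at prior rates of about 65% to 75%, where Fisher's power runs from 78.8% down to 43.6%, and in the fallback it lifts 71% above 80%. Even with one extra control it stays ahead, at 89.2% for 30/31 and 89.1% for 10/11.

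All of that stands as arithmetic and is a reasonable consideration when a test is first chosen. It does not show a fault in this plan. The argument that the pool makes the power unrecoverable fails, because it limits only one arm. The gain also cannot be promised: IEP exclusions can reduce either arm, and the gain changes with the sizes that remain. Adoption has its own costs. A routine implementing the stated definition would have to be named and validated, and the SAP lists only SAS 9.4. SAP section 6.2.1 carries the primary method into the secondary seroresponse rates, so those would change test too, while the threshold, ELISpot and solicited-event comparisons (SAP sections 6.2.1, 6.3.1 and 7.3.1) would stay on Fisher's.

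**Conclusion.** No change. Choosing between two valid exact tests is a fair trade-off, and the plan made the familiar choice, stated it consistently and powered the trial on it. The gain forgone at the planned size and main scenario is 4.5 points (83.3 − 78.8). At the 36% benchmark with 30 per arm it is about 0.01 points. At the 10-per-group contingency it is 14.2 points, the largest among the small sizes checked.

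The plan already limits what rests on this one p-value. It reports an interval for the difference in rates, compares Day 22 titres through the GMR and its interval (SAP section 6.2.1), and repeats the primary analysis in the mITT population. On numbers, Protocol section 4.18 allows that "Subjects who undergo Early Discontinuation at either site before Day 29 may be replaced".

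Timing settles the matter for this trial. SAP section 8 drops the logistic models because response was so high in both groups. Section 2 of the first SAP addendum reports that all subjects had a fourfold rise by the second time point and that both groups stayed at 100%. Replacing the primary test with that knowledge would be post hoc, and with everyone responding in both groups any of these tests gives p = 1.

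The figures assume independent binomial responses, the protocol's 95% naïve rate and two-sided 0.05. Neither test addresses the non-randomised, site-separated groups.

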6.2. Secondary Immunogenicity Endpoints

Secondary immunogenicity endpoints include:

- Anti-CHIKV neutralizing antibodies, determined by luciferase-based assay (NT80), in prior alpha subjects vs. naïve alpha subjects, assessed by
 - Seroconversion rates on Days 8, 29, 57 and 182
 - GMT and GMR on Days 1, 8, 22, 29, 57 and 182
 - The proportion of subjects with titers of at least 40, 100, 160 or 640 on Days 1, 8, 22, 29, 57 and 182
- Anti-CHIKV total antibodies, determined by immunoassay, in prior alpha subjects vs. naïve alpha subjects, assessed by
 - Seroconversion rates on Days 22 and 29 where seroconversion is a 4-fold rise in titer over baseline
 - GMT and GMR on Days 1, 22 and 29

- The proportion of subjects with titers of at least 40, 100, 160 or 640 on Days 1, 22 and 29
- Anti-VEEV neutralizing antibodies, determined by Plaque-Reduction Neutralization Test (PRNT80) assay, in prior alpha subjects vs. naïve alpha subjects, assessed by
 - Seroconversion rate on Days 22 and 29 where seroconversion is a 4-fold rise in titer over baseline
 - GMT and GMR on Days 1, 22 and 29
 - The proportion of subjects with titers of at least 40, 100, 160 or 640 at Days 1, 22 and 29
- Anti-VEEV total antibodies, determined by immunoassay, in prior alpha subjects vs. naïve alpha subjects, assessed by
 - Seroconversion rate on Days 22 and 29 where seroconversion is a 4-fold rise in titer over baseline
 - GMT and GMR on Days 1, 22 and 29
 - The proportion of subjects with titers of at least 40, 100, 160 or 640 at Days 1, 22 and 29

6.2.1. Analysis Methods for Secondary Immunogenicity Endpoints

The same method used for the primary immunogenicity analysis, excluding the estimated difference, will also be used for the secondary analysis of seroresponse rate, comparing the proportion of prior alpha subjects to the proportion of naïve alpha subjects having seroresponse by anti-CHIKV neutralizing antibodies on Days 8, 29, 57 and 182 and by anti-CHIKV total antibodies and anti-VEEV total and neutralizing antibodies on Days 22 and 29.

For the secondary analysis of GMT and GMR, the GMTs and GMRs at the specified time points will be compared for differences between the two study arms (prior alpha vs. naïve alpha) for each type of antibody listed above.

The primary model used for the immunogenicity evaluable population is an analysis of variance (ANOVA), with logarithmically-transformed (\log_{10}) titers as the dependent variable and study arm, age, and gender as the predictor variables in the model. The primary model used for the mITT population is the same except that \log_{10} baseline titer will be added as a predictor if there are subjects with measurable titers in the naïve alpha group at baseline. If any baseline titer is equal to zero, then one will be added to all baseline titers prior to taking the log. The least square means estimated from the ANOVA (or ANCOVA) and their 95% CIs will be back-transformed and reported as the group GMT values. The geometric mean ratio of the prior alpha group to the naïve alpha group, and its 95% CI, will be calculated by specifying a linear contrast between the groups in the model. Since the linear contrast yields a difference between groups in log-transformed space, the difference will be exponentiated to produce a geometric mean ratio of one group to the other. The p-value associated with each model comparison will also be reported. Additionally, the median, minimum and maximum will be summarized based on the non-transformed scale.

An additional analysis of geometric mean of the fold-increase in titer over baseline will be provided. The geometric mean and median fold-increase in titer over baseline will be presented at each visit. To calculate the geometric mean fold-increase and 95% CI, the fold-increase results will be \log_{10} -transformed, the mean and 95% CI of these transformed data will be calculated and then exponentiated to convert to the non-transformed scale. A t-test will be used to compare the \log_{10} -transformed fold increase between the prior alpha and naive alpha subjects. The median, minimum and maximum of the fold-increase in titer over baseline will be summarized based on the non-transformed scale.

The percentage of subjects achieving specified thresholds (40, 100, 160, and 640 anti-CHIKV neutralizing antibody titers), and associated Wilson 95% CIs, will be summarized at Days 1, 8, 22, 29, 57 and 182 for anti-CHIKV neutralizing antibodies and at Days 1, 22 and 29 for anti-CHIKV total, anti-VEEV total, and anti-VEEV neutralizing antibodies. The groups will be compared by pairwise Fisher's exact tests on the percentage achieving each threshold. An additional summary will be provided for the cumulative percentage of subjects reaching the specified thresholds of anti-CHIKV neutralizing antibody titers.

All secondary analyses will be performed for the IEP. The secondary analysis of anti-CHIKV neutralizing antibodies as determined by luciferase-based assay will be repeated on the mITT population.

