STATISTICAL METHODS	
The primary immunogenicity analysis will compare prior alphavirus vaccine recipients to alphavirus-naïve controls on the proportion in each group who seroconvert at Day 22 – three weeks after injection – where seroconversion is defined as a 4-fold or greater rise over baseline in anti-CHIKV neutralizing antibodies as assessed by a luciferase-based assay. The statistical significance of the comparison will be assessed using a Fisher's exact test. The percentage who seroconvert in each group will be presented along with its 95% CI calculated using the Wilson method. Similar methods will be used to compare groups on the percentage of subjects who achieve a titer of at least 40, 160, or 640 at Day 22 (primary time point) and on Days 8, 57 and 182 (secondary time points).
 
GMT will be assessed using an analysis of covariance (ANCOVA) with logarithmically-transformed, anti-CHIKV neutralizing titers (\log_{10}) as the dependent variable and pre-exposure group, age, gender as fixed effects and baseline titer as the covariate in the model. The least square means and 95% CIs estimated from the model will be back-transformed and reported as the group GMT values. The geometric mean ratio (GMR) of the two groups and its 95% CI will be estimated from a model contrast.
 
Similar methods will be used to assess neutralizing and total antibody titers to other alphaviruses (VEEV, WEEV, EEEV) at other time points. Safety will be assessed primarily through the reporting of solicited and unsolicited AEs. Solicited AEs will be summarized for the 7-day period following the injection by the incidence of each type of AE, the first day of its onset, the number of days the AE was reported, and the maximum severity of the AE. Groups will be compared on the incidence of each type of solicited AE using pairwise Fisher's exact tests
 
Unsolicited AEs will be summarized by System Organ Class and Preferred Term, by severity and by potential relationship to the vaccine. Additional displays will summarize any SAEs or AEs that lead to withdrawal or death.

Displays of solicited and unsolicited AEs will present data separately for prior alphavirus vaccine recipients, alphavirus-naïve controls, and for all subjects combined.

Sample Size and Power Considerations

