The GMTs on Days 22 and 29 will be compared for differences between the pre-exposure groups. The GMTs and Geometric Mean Ratios (GMRs) will be analyzed via linear model. The primary model is an analysis of covariance (ANCOVA), with logarithmically-transformed titers (\log_{10}) as

the dependent variable and pre-exposure group, age, gender, as fixed effects and baseline log-transformed titer as the covariate in the model. The least square means estimated from the ANCOVA and their 95% CIs will be back-transformed and reported as the group GMT values. The GMR comparing the pre-exposure groups will be calculated by back-transforming the difference estimated from a linear contrast in the model. The 95% CI for the GMR will be calculated analogously.

The GMTs and GMRs based on antibody titers measured at all other protocol-specified time points will be analyzed as described above for Day 22. The difference in persistence of the antibody response induced after first vaccination at each time point will be visually assessed.

Summaries of both seroconversion and GMT will be presented by age and gender.

Exploratory endpoints (both categorical and continuous) for the heterologous alphavirus analyses will be analyzed descriptively.

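### SAP 6.2.1 drops baseline titer from the GMT model in the immunogenicity evaluable population without listing the change; the VEEV GMR p-value then compares titer levels and does not by itself test the response induced by PXVX0317

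*SAP*

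**What the plan says.** **Protocol.** Section 9.6 (GMT analyses) makes the primary model an ANCOVA on log10 titer, with "the dependent variable and pre-exposure group, age, gender, as fixed effects and baseline log-transformed titer as the covariate in the model". It applies the same approach at the other protocol time points. The synopsis adds: "Similar methods will be used to assess neutralizing and total antibody titers to other alphaviruses (VEEV, WEEV, EEEV) at other time points". The hypotheses in 9.6 are about titer levels: the two parameters "denote the GMT for the prior alphavirus vaccine recipients and the alphavirus-naïve controls, respectively".

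**SAP model.** Section 6.2.1 gives the IEP an ANOVA on log10 titer with "study arm, age, and gender as the predictor variables in the model. The primary model used for the mITT population is the same", except that in the mITT log10 baseline titer "will be added as a predictor if there are subjects with measurable titers in the naïve alpha group at baseline". It then states: "The p-value associated with each model comparison will also be reported".

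**SAP populations.** Section 6.2.1 says "All secondary analyses will be performed for the IEP". Only the anti-CHIKV neutralizing (NT80) analysis is repeated in the mITT. Section 3.1.5 requires naïve IEP subjects to be below an LOD of 15 for CHIKV NT80 and 20 for VEEV PRNT80 at baseline. It sets no such rule for prior recipients.

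**SAP data rules.** Under Section 3.3 a value below LOD becomes LOD/2 for GMT and GMR, but LOD for fold-increase.

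**SAP change list.** Section 8 records a renamed population, the naïve seronegativity rule, an added titer threshold and the dropped logistic regression. The change of GMT model is not there.

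**Analyses that do use baseline.** SAP 6.2 and 6.2.1 plan VEEV seroresponse (a 4-fold rise) on Days 22 and 29 with Fisher's exact test, and GMT and GMR on Day 1 as well as Days 22 and 29. They also say: "An additional analysis of geometric mean of the fold-increase in titer over baseline will be provided". That analysis gives each arm's geometric mean fold-increase with a 95% CI, and a t-test between arms.

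**The concern.** The secondary objective (Protocol 2.2) concerns antibody responses induced by PXVX0317. The second study question in Protocol 1.3 asks whether the vaccine boosts existing responses, or induces new ones, to other alphaviruses. A between-arm comparison of post-vaccination titers, with no baseline term, contains whatever difference existed on Day 1.

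For VEEV neutralizing antibody the population rules favour such a difference. One arm must be below LOD; the other is chosen for earlier alphavirus vaccination, though not necessarily against VEEV. The GMR p-value can then be significant when nobody responded. It can also be unremarkable when only the naïve arm responded. Because the SAP calls this model primary and does not say which analysis answers the induced-response question, a difference that preceded vaccination could be read as a vaccine effect.

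**Working it through.** **1. The two models side by side.**

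| Titer | Protocol 9.6 and synopsis | SAP, IEP | SAP, mITT |
|---|---|---|---|
| Anti-CHIKV NT80 | arm, age, gender, log10 baseline | arm, age, gender | baseline added if any naïve subject is measurable at Day 1 |
| Anti-CHIKV total | same | arm, age, gender | not analysed |
| Anti-VEEV total and neutralizing | same (similar methods) | arm, age, gender | not analysed |

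**2. The plan's own figure.** The documents give no effect size or power for the VEEV GMR. Their power figure is for primary seroconversion (95% v 65%, 30 per arm): 80% stated, 78.8% by exact enumeration of Fisher's test. It is not affected here.

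**3. VEEV neutralizing antibody with no response in either arm.** The documents give the LOD (20) and so the imputed value (10). Assume a share s of the prior arm is seropositive with geometric mean titer G. Ignoring seropositive values that fall below LOD,

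log10 GMR = s × log10(G/10), the same on Day 1 and on Day 22.

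| s | G | s × log10(G/10) | GMR |
|---|---|---|---|
| 20% | 40 | 0.120 | 1.32 |
| 20% | 320 | 0.301 | 2.00 |
| 50% | 40 | 0.301 | 2.00 |
| 50% | 320 | 0.753 | 5.66 |
| 74% | 80 | 0.668 | 4.66 |
| 100% | 320 | 1.505 | 32 |

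As a rough guide to significance, take a 4-fold Day 1 gap and log10 SD 0.5. The standard error is 0.5 × √(2/30) = 0.129, and 0.602/0.129 − 1.96 = 2.70, so p<0.05 has probability about 99.7%.

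**4. Simulation of the same case.** Inputs: 30 per arm, SAP 3.3 rules, log10 SD 0.5, assay SD 0.15, seronegative latent titer 5, G from 40 to 320, 2,000 runs per setting.

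| Seropositive in prior arm | ANOVA GMR | ANOVA p<0.05 |
|---|---|---|
| 20% | 1.3–2.0 | 50–82% |
| 50% | 2.0–5.6 | at least 99.8% |
| 74–100% | 2.8–32 | 100% |

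In all 16 settings the post-vaccination GMR equals the Day 1 GMR within 1%. The fold-increase t-test gives a ratio of 1.00 and 2–6% rejections. The protocol's ANCOVA gives GMR 1.01–1.34 and 0–35% rejections. It does not fully repair VEEV, because naïve baselines are all imputed as 10: the slope comes from the prior arm alone and is diluted by assay error.

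**5. The opposite error.** Let 74% of the prior arm be seropositive with GMT 80 and unchanged, and let only the naïve arm rise 8-fold, from latent 5 to 40. The GMR becomes 4.66 × 10/40 = 1.17. Simulation gives 1.16–1.18, with p<0.05 in 8–9% of runs. ANCOVA and the fold-increase t-test reject in 100%.

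**6. Limits of the baseline-referenced analyses.** For fold-increase, a start below LOD counts as 20.
- The 8-fold rise in step 5 is recorded as 40/20 = 2-fold. It misses 4-fold seroresponse, which for such a subject needs at least 4 × 20 = 80, but it shows in the naïve arm's own fold-increase.
- A true 4-fold rise from 5 to 20 is recorded as 20/20 = 1, against 4 for a prior subject going from 80 to 320.
- With equal true rises in both arms and latent titer 2.5 or 5, the simulated between-arm fold ratio is 1.12–1.99 for a 2-fold rise (44–100% rejections) and 1.22–3.93 for a 4-fold rise (45–100%).
- The prior arm's own fold-increase CI excludes 1 in 1–6% of runs with no response, and in 46–100% after a 2-fold rise.

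**7. Total anti-VEEV (illustrative; log10 SD 0.4, assay SD 0.15).** With no response and baseline ratios of 1.5, 2 and 3, ANOVA rejects in 35%, 77% and 98.5%; ANCOVA in 7%, 11% and 15%; fold-increase in 4–6%. With equal baselines and a true 1.3-fold difference in rise, power is 18% (ANOVA), 57% (ANCOVA) and 54% (fold-increase).

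**8. Anti-CHIKV NT80 in the IEP.** With no cross-reactive baseline titers in the prior arm, the two models coincide. With 10–50% of that arm cross-reactive and a baseline slope of 0 to 0.6, the ANOVA GMR is 1.00–1.55 (5–38% rejections), against 1.00–1.01 (4–6%) for ANCOVA.

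**The case against.** The best defence has four parts.

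- **Levels were always the hypothesis.** Protocol 9.6 states it in terms of GMTs, so a level comparison is legitimate. This stands, which is why the p-value needs a label and not removal.
- **The covariate does little for VEEV neutralizing antibody.** Once naïve baselines are fixed below LOD, the slope rests on one arm, and step 4 shows ANCOVA still rejecting in up to 35% of null runs. This may be why the term was dropped, but the SAP does not say so. The reasoning also does not reach total antibody, for which Section 3.1.5 sets no baseline requirement.
- **The SAP already has baseline-referenced VEEV analyses.** They include the protocol's own 4-fold seroconversion endpoint. The Day 1 GMR belongs to the same endpoint as the later GMRs, and planned figures show VEEV titer and fold-increase over time, so a Day 1 gap would be visible. A reader might infer that the plan has no test of induced VEEV response; the documents contradict that.
- **The sizes are assumed.** The documents give the LODs and a 26% TC83 non-response rate, which is not the share now below LOD. The percentages illustrate and do not predict.

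Three further inferences are not supported. The between-arm fold-increase t-test should not be made decisive, because equal true rises can give a ratio above 1 (step 6). Addendum 2 uses the same ANOVA for heterologous CHIKV strains, but Protocol 9.6 plans exploratory heterologous endpoints descriptively, so no ANCOVA was promised there. Nor does the conditional mITT rule look at outcomes: it uses pre-vaccination naïve titers and concerns anti-CHIKV NT80 only.

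**Conclusion.** The concern holds for secondary endpoints. The model differs from the protocol's, Section 8 neither lists nor justifies the change, and no VEEV or total-antibody GMR is baseline-adjusted. For VEEV neutralizing antibody, the Day 22 and 29 GMR and p-value carry any Day 1 difference and do not by themselves test induced response. They can mislead in either direction. The direction of the first error depends only on prior recipients retaining measurable VEEV titers; its size depends on titers the documents do not give.

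A reader might go further and doubt the primary result. The documents do not support that: the primary endpoint is Day 22 anti-CHIKV seroresponse by Fisher's exact test and does not use this model. For anti-CHIKV NT80 GMRs the effect is probably small, and nil without cross-reactive titers in the prior arm. Severity: minor to should-fix.

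**What to change.** 1. List the change from ANCOVA to ANOVA in SAP Section 8 with its reason, labelled post-lock if made then.
2. Label the VEEV GMR p-value as a comparison of titer levels and read it beside the Day 1 GMR. State that induced VEEV response is judged from the protocol's 4-fold seroresponse and from each arm's own geometric mean fold-increase with 95% CI. Treat the between-arm fold-increase t-test as supportive. Say that the LOD rule understates rises starting below LOD, a limit that seroresponse shares. Report the number below LOD in each arm at Day 1 and Days 22 and 29.
3. Restore log10 baseline titer at post-baseline visits for total antibody and anti-CHIKV NT80 wherever baseline varies, with Day 1 itself analysed without it. Note that some bias remains if noisy baselines differ between arms (up to 21% rejections at a baseline ratio of 3 and assay SD 0.20). For VEEV neutralizing antibody, give ANCOVA only as a sensitivity analysis.

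The cost is wording, table labels, one model term and a little more table work, with no new data. The VEEV GMR will look less striking. If the results are already known, naming the basis for judgement now is post hoc and should be reported as such.
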